3.5 Recruitment

A sampling frame that include all T2DM Malay patients who obtained the supply of the medications from the two study sites (HCKS and HCPJ) for more than three months, is obtained prior to the study. The method of obtaining sampling frame is done through screening all the prescriptions prescribed by the medical specialists, medical officers or health officers from both study sites within the period of 1st February 2017 to 30th April 2017. Information that could be obtained through prescription screening include the diagnosis and medications of the patients, name and age. Malay patients could be identified based on their name, with male having the word

“bin” or “b” and female having the word “binti” or ‘bt’ among their name characters. However, the exact ethnicity of the respondents will be confirmed in subsequent screening. As such, all potential respondents who are Malay T2DM patients will be approached during the screening phase.

After that, approximately one month prior to the actual study which is during 1st – 30th June 2017 (T0 screening), will be the screening phase to identify potential respondents for this study with structured screening form as in Appendix A. An 8-items MALMAS medication adherence scale that had been validated among Malaysian with T2DM (Chung et al. 2015), will be administered to obtain the adherence score which enable the researchers to evaluate the eligibility of the prospective respondents. Patients who are having middle and low medication adherence level (MALMAS score < 6) and fulfill all the inclusion and exclusion criteria will be provided with informed consent and study information sheet (APPENDIX B). Those who agree to participate will be informed about the KYM-TIFH and they will be asked to choose a date during the campaign to attend the program. After they choose the date they prefer, their name will be recorded in the “List of Participants” (APPENDIX C) with a specific code assigned. Notably, patients are not informed of their group assignment and thus are not aware of the differences between intervention group and control group. Besides, none of the recruiters who are the pharmacist staff at both health clinics, are aware of subsequent treatment allocation throughout the recruitment stage, to ensure allocation concealment. All research materials that contain patients’ information will be coded and kept by principal investigator to maintain confidentiality of respondents.

3.6 Randomization and Blinding

The Sarawak Research Society who is independent from this study team will be appointed to carry out the simple randomization. The “List of Participants” will be handed over to the chairman of the Society to carry out the randomization. The randomization will be conducted using online randomization program available at <http://www.graphpad.com/quickcalcs/index.cfm> as recommended by Suresh (2011). After that the participants’ list with their code and group assignment will be kept by the chairman of the Society without informing any of the researchers, facilitators and respondents to assure the blinding of three parties about the treatment allocation. On the day of the intervention, the chairman and the authorized committee member of the Society will register the attendance of respondents and inform them about the actual venue of the program. Each HCKS and HCKS will have two venues prepared and available during the period of the study with one venue allocated for intervention group and the other one allocated for control group. None of the participants will be aware of the difference between the venues assigned while facilitators do. However, participants will be able to know whether they are assigned to control group as there will not be any form of information provided to the participants in control group. Hence, the blinding of participants and facilitators end at the stage of the intervention.

For the blinding of researchers, it will be continued towards the stage of publication. During the post-intervention follow up, the researchers still are blinded on the allocation of participants, as the participant list with group allocation is kept by the chairman of the Society. None of the instruments distributed to the participants will disclose their name and their group assignment to assure the blinding among researchers who do the data analyses. Only after the results of this

study is published, the blinding or the codes will be broken through the return of the participants' list to the principal investigator. The randomization codes will be maintained by the chairman of the Society throughout the study without disclosing it to the researchers or the participants.

No procedure of breaking code is necessary for this study as the intervention of this study is educational and does not involve investigation medicinal product (IMP). Thus, the risk of suspected unexpected serious adverse reaction (SUSAR) or serious adverse event (SAE) would be at minimum or none. However, should any SAE or SUSAR happen during the study, the principal investigator will be reported to the MREC and the physicians of the health clinic to rule out the possibility of such condition is due to this study before proceeding to break code.

Figure 7 shows the flow of participants and randomization throughout the study.

[figure not shown]

Figure 7: Flow of participants and randomization of this study.

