3.7 Sample size

We are planning a study of a continuous response variable from independent control and experimental subjects with 1 control per experimental subject. In a previous study (Butt et al. 2016), the response within each subject group was normally distributed with standard deviation 1.8. If the true difference in the experimental and control means is 1, we will need to study 69 experimental subjects and 69 control subjects to be able to reject the null hypothesis that the population means of the experimental and control groups are equal with probability (power) 0.9 (Dupont and Plummer 1998). By estimating 30% of dropout or incomplete data, a minimum sample size 180 with 90 for both groups are pre-determined for each study sites.

On the other hand, to test the integrated model as mentioned in second objective, with effect size f square equal to 0.15, α error probability equals to 0.05, power equals to 0.95 and total number of predictors equal to 3, total sample size required will be 170 (Faul et al 2009). Assuming 30% of dropout or incomplete data, a minimum sample size 221. As a result, a total minimum sample size of 442 with 221 for both groups are acquired.

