3.8 Intervention Design

The KYM-TIFH of this study was formulated and employed by the researchers of this study who work at Pharmaceutical Services Division of Sarawak State Health Department in late 2016 under the national campaign “Know Your Medicine”. It aims to promote medication adherence among T2DM Malay patients due to prevailing nonadherence among them as mentioned earlier. The official name of the intervention is “Kenali Ubat Anda – Ambil demi Kesihatan” in Malay language or “Know Your Medicine – Take it for Health” in English with abbreviation KYM-TIFH. It was specifically designed to complement the individual approach in improving

medication adherence among T2DM Malay patients. This is because group-based intervention can engage more patients at once and serves as building the fundamental capability of patients to adhere with prescribed medications within shorter period as compared to individual approach. Mattson and Hall (2011) advocated that SGBI has numerous irreplaceable benefits that individual approach might not have, including (1) validation; (2) normalization of experience; (3) reduction of isolation; (4) sense of belonging; and (5) enhanced self-esteem. The number of participants for each session of the SGBI is fixed between 20 to 24 participants. The SGBI is only conducted for once with three hours (180 minutes) long and facilitated by one main facilitator and three assistant facilitators. The KYM-TIFH nonetheless had considered the barriers towards medication adherence among T2DM patients (as in Table 1) by incorporating several strategies in designing the program.

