3.8.5 Study Timeline

The researchers of this study will begin to screen and recruit respondents between 12nd to 23th June 2017. Besides, pre-test on the measurement scales will be conducted prior to actual data collection. The actual intervention will be on 17th to 21st July 2017 for HCKS and on 24th to 28th July 2017 for HCPJ. The post 1 month measurement of actual medication adherence will be carried out on 21st to 25th August 2017 for HCKS respondents and on 28th to 31st August 2017 for HCPJ respondents. The study timeline is illustrated as in Figure 11.

[figure not shown]

Figure 11: Time of interventions. MALMAS/IE: Medication Adherence Scale plus Inclusion & Exclusion Criteria Screening (Appendix A); TPB-IMB: Scale for Integrated Model of Theory of Planned Behaviour with Information-Motivation-Behavioural Skill Model (Appendix D); KYM-TIFH: “Know Your Medicine- Take if for Health” program; FGD/SI: Focus Group Discussion or Semi-Structured Interview; KS-HC: Kota Samarahan Health Clinic; PJ-HC: Petra Jaya Health Clinic

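### Simple randomisation after participants have picked their own date does not ensure sessions of 20 to 24, or balance of the arms within clinic and date

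*Protocol*

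**What the plan says.** - **Order of events.** Under section 3.5, participants who consent are told about the programme and "they will be asked to choose a date during the campaign to attend the program". Their names then go on a coded list. No maximum per date is given.
- **Allocation.** Under section 3.6 the list "will be handed over to the chairman of the Society to carry out the randomization", and the society "will be appointed to carry out the simple randomization" with an online program. The text names no block and no stratum. It does not say whether there is one list or one per clinic, and the participant-flow figure (Figure 7) is not available to this review.
- **Session size.** Section 3.8 states: "The number of participants for each session of the SGBI is fixed between 20 to 24 participants". Section 3.8.3 repeats the range and bases staffing on it, with one main and three assistant facilitators looking after 5 to 6 participants each.
- **Dates.** Section 3.8.5: "The actual intervention will be on 17th to 21st July 2017 for HCKS and on 24th to 28th July 2017 for HCPJ". That is five days per clinic. The number of sessions per day is not stated.
- **Arm sizes.** Section 3.7 plans "with 1 control per experimental subject", sets "a minimum sample size 180 with 90 for both groups are pre-determined for each study sites", and ends with "a total minimum sample size of 442 with 221 for both groups are acquired".

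**The concern.** The protocol fixes the size of each session but names an allocation method that leaves it to chance. Once people are attached to a date and then allocated without restriction, the number from that date in the intervention arm is a random count. The text gives no rule for a date that draws 16 or 28.

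Two things are at stake. The first is delivery to specification. A three-hour group programme staffed for 5 to 6 participants per facilitator would run with 4 or 7 per facilitator at those sizes (16/4 and 28/4), against the aim in section 3.13 of the same treatment dose within a condition. The second is balance. Clinic and date are the factors that structure delivery, and simple randomisation balances the arms on neither except on average.

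**Working it through.** **1. The plan's own figure.** Inputs from section 3.7: SD 1.8, difference 1, power 0.9. Alpha is not stated for this calculation, so two-sided 0.05 is assumed.

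n per arm = 2 × 1.8² × (1.960 + 1.282)² / 1² = 68.1, rounded up to 69, as stated. Then 69 × 1.3 = 89.7, which gives the 90 per arm per site.

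**2. Session size under simple randomisation.** Let n be the number booked on a date. Assume one intervention session per date and full attendance. The intervention count is X ~ Binomial(n, 0.5), and the quantity needed is P(20 ≤ X ≤ 24).

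| Booked | P(below 20) | P(20 to 24) | P(above 24) | 95% range of X |
|---|---|---|---|---|
| 36 | 0.69 | 0.29 | 0.01 | 12–24 |
| 40 | 0.44 | 0.49 | 0.08 | 14–26 |
| 44 | 0.23 | 0.55 | 0.23 | 16–28 |
| 48 | 0.10 | 0.46 | 0.44 | 17–31 |

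The total of 442 over two clinics and five dates averages 442/10 = 44.2 per date, so 44 is the natural case. It is also the most favourable row.

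**3. If the program forces equal totals.** X is then hypergeometric. With 44 booked, P(20 to 24) is 0.57 when 221/221 is forced over 442, and 0.60 when an equal split is forced within a clinic of 221. Fixing the totals leaves the dates uncontrolled.

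**4. Arm size per clinic.**
- With 442 recruited, about 221 per clinic: P(both arms at least 90) = 0.995 at one clinic and 0.995² ≈ 0.99 at both. The 95% range for one arm is 96 to 125.
- With recruitment stopped at 180 per clinic, both arms reach 90 only if the split is exactly 90/90, which has probability 0.059. The 95% range is 77 to 103.

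**5. Effect on power.** At 180 participants, power = Φ(1/SE − 1.96), with SE = 1.8 × √(1/n₁ + 1/n₂).
- 90/90: SE = 0.268, power 0.961.
- 77/103: SE = 0.271, power 0.958.

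**6. Would blocking within date be enough?** Assume 221 at a clinic choose freely among five equally popular dates. By simulation, a session lands in 20 to 24 with probability 0.60 when blocked within date, against 0.43 under simple randomisation. With 180 per clinic (36 expected per date, so 18 per arm) blocking gives 0.28 against 0.29. Bookings therefore need controlling too.

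**7. No-shows.** The attendance rates below are assumptions; the protocol gives none. Attenders ~ Binomial(m, a), with m allocated per session after blocking.

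| Booked → allocated m | P(20 to 24), a = 0.95 | a = 0.90 | a = 0.85 |
|---|---|---|---|
| 40 → 20 | 0.36 | 0.12 | 0.04 |
| 44 → 22 | 0.91 | 0.62 | 0.34 |
| 48 → 24 | 0.99 | 0.92 | 0.71 |

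For comparison, simple randomisation of 44 gives 0.52, 0.46 and 0.36 at the same rates. At 44 booked the gain from blocking disappears by 85% attendance. At 48 it persists: simple randomisation gives 0.52, 0.53 and 0.48.

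**The case against.** The best defence is that simple randomisation of several hundred people is an accepted method, and that most of the harms one might infer do not follow.

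- **That 90 per arm per site cannot be delivered.** Not supported. The final minimum is 442, and at that size the target is met almost always. It is at risk only if recruitment stops near 180 per clinic.
- **That an intervention arm below 221 is a failure.** Not supported for the comparison of arms. Section 3.7 needs 69 per arm for that; the larger total comes from the calculation for the predictive model.
- **That precision suffers.** The power difference is 0.003 at a 77/103 split.
- **That off-size sessions force moves which break the randomisation.** The protocol provides for no such moves. Moving someone to another date within the allocated arm leaves the randomisation intact; only a change of arm would damage it.
- **That all ten sessions would comply only 0.25% of the time.** This figure (0.55 to the tenth power) assumes one session per date, exactly 44 booked on every date and full attendance. The documents state none of these.

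The defence is also right that Figure 7 and the program's behaviour are unseen, and that separate lists per clinic are possible. Neither rescues the session size: separate lists, or equal totals from the program, still leave the split within a date to chance. What remains is a mismatch between a fixed session size and a method that does not control it.

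**Conclusion.** The point holds as a matter of delivery and balance. Sections 3.5, 3.6, 3.8 and 3.8.3 do not fit together: dates are chosen without a stated cap, allocation is unrestricted, and session size is fixed. With about 44 booked, a session meets its specification with probability near 0.55, or up to 0.60 if totals are forced equal. This rests on one intervention session per date, which agrees with the single intervention venue per clinic in section 3.6 but is not stated, and on full attendance.

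It is not a threat to power, and it is not evidence that allocation would be compromised. It is a cheap improvement worth making before the list is handed over.

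**What to change.** In section 3.6, replace simple randomisation with 1:1 allocation in permuted blocks, stratified by clinic and chosen date. The society receives the list after dates are recorded and before anyone is allocated, and recruiters do not know the allocation, so blocking carries no risk of predictability here.

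In section 3.5, add a booking cap per date, set towards the upper end of 40 to 48 to leave room for no-shows. Five dates at 48 hold 240 per clinic, enough for 221. Because 221 over five dates averages only 44.2, dates should be filled with the lower limit in mind as well as the cap. At 180 per clinic, four dates averaging 45 would suit better than five averaging 36.

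State the number of sessions per day, and what happens when attendance falls outside 20 to 24. Include clinic in the analysis as a stratification factor; this follows from the changed design, and its detail can sit in the SAP.

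Cost: slightly more bookkeeping for recruiters and the society, and some participants not getting their first-choice date. Session size will still vary with attendance on the day.

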3.7 Sample size

We are planning a study of a continuous response variable from independent control and experimental subjects with 1 control per experimental subject. In a previous study (Butt et al. 2016), the response within each subject group was normally distributed with standard deviation 1.8. If the true difference in the experimental and control means is 1, we will need to study 69 experimental subjects and 69 control subjects to be able to reject the null hypothesis that the population means of the experimental and control groups are equal with probability (power) 0.9 (Dupont and Plummer 1998). By estimating 30% of dropout or incomplete data, a minimum sample size 180 with 90 for both groups are pre-determined for each study sites.

On the other hand, to test the integrated model as mentioned in second objective, with effect size f square equal to 0.15, α error probability equals to 0.05, power equals to 0.95 and total number of predictors equal to 3, total sample size required will be 170 (Faul et al 2009). Assuming 30% of dropout or incomplete data, a minimum sample size 221. As a result, a total minimum sample size of 442 with 221 for both groups are acquired.

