2.3 Hypotheses

Based on the first specific objective, two hypotheses to be tested are:

H1a: There is significant difference of medication adherence level among participants before and after the intervention.

H1b: There is significant difference of medication adherence level after the intervention between participants from intervention group and control group.

Based on the second specific objective, six hypotheses to be tested are:

H2a: There is a significant relationship between attitude to adherence and intention to adhere.

H2b: There is a significant relationship between subjective norm to adherence and intention to adhere.

H2c: There is a significant relationship between perceived behavior control to adherence and intention to adhere.

H2d: There is a significant relationship between perceived behavior control to adherence and medication adherence.

H2e: There is a significant relationship between intention to adherence and medication adherence.

H2f: There is a moderating effect by adherence information between intention to adhere and medication adherence.

Based on the third specific objective, five hypotheses to be tested are:

H3a: There is significant difference of attitude to adhere after the intervention between participants from intervention group and control group.

H3b: There is significant difference of subjective norm to adhere after the intervention between participants from intervention group and control group.

H3c: There is significant difference of perceived behavioural control to adhere after the intervention between participants from intervention group and control group.

H3d: There is significant difference of intention to adhere after the intervention between participants from intervention group and control group.

H3e: There is significant difference of adherence information after the intervention between participants from intervention group and control group.

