This chapter depicts the research paradigm and methodology employed to achieve the three specific objectives of this study. For the first research objective, which is to measure the effectiveness of the KYM-TIFH, positivist approach with experimental study design is best suited. In specific, experimental study with randomized controlled trial (RCT) design is employed as RCT is positioned at higher level of evidence-based medicine pyramid after case studies, case-control and cohort studies (Murad et al. 2016). Nevertheless, the findings from the RCT on the effectiveness of the KYM-TIFH will be triangulated by the findings from subsequent focus group discussion (FGD) and semi-structured interview (SSI) which employ interpretivist or qualitative approach. The aim of the interpretivist approach is to obtain the experience and attitudes of respondents about the KYM-TIFH in a flexible and iterative manner (Berg and Lune 2004; Smith 2002).

For the second objective, which is to test the predictive capacity of the integrated model on medication adherence, positivist approach with cross-sectional analysis is best suited. The point of assessment will be at the end of the trial. For the third objective, which is to test the impact of KYM-TIFH on the psychosocial variables that lead to medication adherence, the positivist approach with prospective analysis to examine how the psychosocial variables change before and after the intervention and cross-sectional analysis to examine whether there is significant difference of the change in psychosocial variables between participants from intervention group and control group.

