3.3 Study setting- the study sites or clusters

The selected study sites that would enable the researchers of this study to engage with the targeted population are Petra Jaya Health Clinic (PJ-HC) and Kota Samarahan Health Clinic (KS-HC) that are funded by Malaysian government. Residents who reside at Petra Jaya and Kota Samarahan are able to access to quality healthcare services at the Health Clinic Petra Jaya (PJ-HC) and Health Clinic Kota Samarahan (KS-HC) respectively. Both clinics have medical specialist, medical officers, pharmacists, nurses and other allied health professionals to run the services such as emergency unit, out-patient unit, maternal & child clinic, pathology unit, X-Ray unit, disabled children development unit, counselling service unit and diabetes unit (Borneo Post Online 2014; Chew et al. 2017). Patients who suffered from T2DM can be diagnosed and get continuous consultations, medications and monitoring of the disease at the clinics. Nevertheless, both clinics will be run by a pharmacist who is specifically trained to run a diabetic MTAC (i.e. DMTAC) who shall also be referred to as a pharmacist in-charge of the DMTAC. He/she shall address any medication-related problems encountered by the patients in order to ensure that they will become adherent towards their complex multiple-medication treatment regimens. Only patients who deemed to have problems with adhering their medications will be referred by doctors to attend DMTAC. However, due to constraint in manpower, each diabetic pharmacist would only able to cater certain number of patients referred. Thus, the KYM-TIFH was designed with an aim to complement rather than competing the existing efforts.

With the aim to recruit suitable participants that could yield highly generalizable data to the studied population, PJ-HC and KS-HC are chosen as the study sites to recruit respondents and collect data. Moreover, the KS-HC had been included as one of the KYM-TIFH campaign site on 17-21 July 2017 while PJ-HC will be on 24-28 July 2017. Thus, the researchers incorporate this

study during the period of KYM-TIFH campaign by obtaining prior approval and financial support from Head of Department of the Sarawak Pharmaceutical Services Division.

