3.11.3 Data analysis for second objective

The second objective is to test the predictive capacity of the integrated model. For that, path analysis using Partial Least Square-Structural Equation Model (PLS-SEM) with SmartPLS 3.0 software will be conducted.

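### Protocol 3.7: the inputs given for the integrated model require 119 participants before loss, not 170, and the step from 221 to 442 is not explained

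*Protocol*

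**What the plan says.** Section 3.7 contains two calculations.

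- **Adherence outcome.** 69 per group are needed. With 30% loss this becomes "a minimum sample size 180 with 90 for both groups are pre-determined for each study sites". Section 3.3 names two sites: "PJ-HC and KS-HC are chosen as the study sites to recruit respondents and collect data".
- **Integrated model (objective 2).** The inputs are "with effect size f square equal to 0.15", alpha 0.05, and "power equals to 0.95 and total number of predictors equal to 3, total sample size required will be 170". An allowance of 30% takes 170 to 221. The section then concludes: "As a result, a total minimum sample size of 442 with 221 for both groups are acquired".

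On what the second calculation is for, section 3.11.3 says "The second objective is to test the predictive capacity of the integrated model" and plans one PLS-SEM path analysis. The Chapter 3 overview says that to "test the predictive capacity of the integrated model on medication adherence, positivist approach with cross-sectional analysis is best suited", with assessment at the end of the trial. The hypotheses in section 2.3 (H2a to H2f) describe one model. None of these places mentions a separate fit by group or by site.

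**The concern.** The protocol fixes all four inputs and the result, so the result can be checked, and it does not follow. The chain 170, 221, 442 also carries a figure described as a total into a per-group or per-site figure with no linking argument. Because 442 is the trial's stated minimum enrolment, an ethics committee or later reader should be able to rebuild it from section 3.7 and cannot. What is at stake is the justification of the enrolment figure, not the adequacy of the sample.

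**Working it through.** **1. The protocol's own chain.** 170 × 1.3 = 221 and 221 × 2 = 442. These steps are arithmetically consistent with each other. The starting value of 170 is the one that fails.

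**2. The requirement from the stated inputs.** The test is the overall F test of a multiple regression with f² = 0.15, alpha = 0.05 and u = 3 predictors (all from 3.7). Denominator degrees of freedom are v = N − 4, noncentrality is λ = f² × N, and power = P[F′(u, v, λ) > F(0.95; u, v)].

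| N | λ = 0.15 × N | v | Power |
|---|---|---|---|
| 118 | 17.70 | 114 | 0.9492 |
| 119 | 17.85 | 115 | 0.9510 |
| 170 | 25.50 | 166 | 0.9931 |

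The smallest N reaching 0.95 is 119. The stated 170 is 170/119 = 1.43 times that.

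**3. Whether another standard calculation gives 170.** With f², alpha and the number of predictors as stated:

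- noncentrality f² × v: 123
- R²-increase tests: 89 to 119
- single-coefficient t test: 89 two-sided, 74 one-sided
- power raised to 0.99: 161

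Changing an input comes closer: 9 predictors give 166 and 10 give 172; alpha 0.005 gives 173; f² of 0.102 gives 173 and of 0.105 gives 168; 4 predictors at alpha 0.01 give 169. The protocol states none of these values.

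**4. A possible origin of 170.** 119/(1 − 0.30) = 170.0. This would mean that 170 already contains the 30% allowance and that the ×1.3 applies it again.

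**5. What 442 delivers for the model.** 442 × 0.70 = 309.4, so 309 completers. In one pooled fit with 3 predictors the power is above 0.999.

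**6. Minor: the inflation of 69.** 69 × 1.3 = 89.7, rounded to 90. But 90 × 0.70 = 63, which is below 69. The correct inflation is 69/0.70 = 98.6, rounded up to 99. If the target stays per group at each site, that is 2 × 99 = 198 per site and 2 × 198 = 396 over two sites, in place of 2 × 180 = 360. Both are below 442. Even the uncorrected figure leaves 2 × 90 × 0.70 = 126 per group over the two sites, against 69 needed.

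**The case against.** The best defence concerns the doubling. The adherence calculation just before it is set for each site, and there are two sites, so 442 could be 221 at each of two sites. The wording itself points rather to 221 in each group. Whether the path model is fitted pooled, by group or by site may also be settled in a statistical analysis plan that is not at hand. This stands in part: a reader might infer that the doubling is baseless, and the documents do not go that far. They show only that 3.7 gives no reason and that the protocol describes one model. Even a separate fit in each half would need 2 × 170 = 340 after one allowance for loss, so 442 still would not follow from the inputs.

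Three further readings are tempting and are not supported.

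- **That loss was counted twice, as a fact.** The match of 119/0.70 with 170 is exact, but the text presents 170 as the figure before loss.
- **That enrolment should fall to 360.** That figure rests on the faulty inflation of 69. Corrected on the protocol's own per-site basis, it is 396.
- **That three predictors is the wrong count.** H2f ("There is a moderating effect by adherence information between intention to adhere and medication adherence") adds an interaction, and a four-predictor adherence equation would need 129. But three predictors match H2a to H2c, so moving to four would re-specify the sizing rather than correct an error.

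It is also fair to say that nothing in the trial's conclusions changes, since the model has more than its intended power on every reading.

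**Conclusion.** The point holds as a correction to stated figures. The inputs in 3.7 require 119 before loss and 170 after a 30% allowance applied once; the protocol gives 170 and 221. The further step to 442 is unexplained. The errors in the model calculation run only towards a larger sample, and the under-inflation of 69 is absorbed by the use of two sites, so no objective is put at risk.

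The conclusion assumes that the overall regression F test is the calculation meant. The inputs are in that form and the section cites the G*Power 3.1 paper for it; the other standard tests tried do not give 170 either.

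**What to change.** Revise the text of section 3.7 only:

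1. State the model requirement as 119 before loss for the 3 predictors given.
2. Apply the 30% allowance once, by division: 119/0.70 = 170 in total.
3. Then do one of two things. Either state why 221 is doubled (per group or per site) and keep 442 as the planned enrolment, with the model power it gives: above 0.999 with 309 completers in a pooled fit. Or no longer present 442 as the size that the model requires.
4. Minor: replace 90 by 99 as the inflation of 69. If the target remains per group at each site, give 198 per site and 396 over two sites.

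Do not add two-sample t-test power figures for the adherence outcome when revising. Section 3.11.2 plans rank tests on adherent versus non-adherent status, which such figures would not describe.

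The cost is a few sentences. Planned enrolment need not change, because 442 covers every corrected requirement.
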